### 9.4.3 Secondary outcomes

- 3) Change in caregiver burden as measured with the Zarit Burden Interview;
- 4) Change in emotion regulation/coping styles as measured with the Cognitive Emotion Regulation Questionnaire (CERQ);
- 5) Change in uncertainty tolerance as measured with the Intolerance of Uncertainty Scale (IUS);
- 6) Change in mindfulness as measured by the CAMS-R.
- 7) Change in perceived social support among caregivers as measured with the PROMIS social support short forms for emotional, informational, and instrumental support;
- 8) Change in family conflict around caregiving as measured by the Family Conflict Scale;
- 9) Change in emotional distress as measured by the anger and anxiety PROMIS short forms;
- 10) Change in perceived health as measured by the PROMIS global health short form;
- 11) Change in hopefulness and optimism as measured by the PROMIS meaning and purpose short form;
- 12) Change in caregiver self-efficacy as measured by the PROMIS self-efficacy short forms.
- 13) (Qualitative) Evaluation of the comfort with and willingness to adopt technologies to access mindfulness practices and existing caregiving educational resources.

## 9.5 Data Analyses

This is a single-arm pilot feasibility study with one baseline and one post-intervention measure.

Quantitative variables

For all quantitative questionnaire measures (outcomes 3-11), the change in the measure from baseline to post-participation is the outcome. First, we will examine variable distributions and missing data patterns. Next, we will conduct exploratory, descriptive analyses to assess *patterns of change* associated with participation in the programs for each of the variables including proximal mediating outcomes, intermediate outcomes (secondary stressors), and distal health outcomes. Because all analyses are exploratory, we will next perform bivariate assessments utilizing a paired t-test, analyzing caregivers and care partners separately. We do

not plan to adjust for multiple comparisons, but will interpret results conservatively and with great caution.

We will also explore the use of multivariable methods to enable us to control for variables that could influence the outcomes. Adjusted models will utilize repeated measures mixed models with individuals nested in families as random effects. We will control for the baseline FAST score (severity of dementia) and the relationship to the care recipient (spouse, adult child, other relative). In this small study (32 dyads), it will not be possible to formerly assess subgroups defined by gender. However, we will produce descriptive statistics by gender and age group.

We plan to invoke an intention-to-treat analysis in dealing with missing data using multiple imputation or full information maximum likelihood methods.

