### **1.2 Secondary Objectives**

SPECIFIC AIM 2: To explore, on a preliminary basis, the effects of the training on caregiver burden and relevant secondary outcomes for both caregiving team members, including:

Hypothesis 1: Compared with baseline levels, we hypothesize that mindfulness training will reduce caregiver burden (Zarit Burden Interview).

Hypothesis 2: Compared with baseline levels, we hypothesize that mindfulness training will improve emotion regulation by increasing positive coping styles (acceptance, positive refocusing, positive reappraisal) and decreasing negative coping styles (rumination, catastrophizing, self-blame) as measured by the Cognitive Emotion Regulation Questionnaire.

Hypothesis 3: Compared with baseline levels, we hypothesize that mindfulness training will increase tolerance of uncertainty as measured by (an adapted form of) the Intolerance of Uncertainty Scale.

Hypothesis 4: Compared with baseline levels, we hypothesize that training in mindful communication will increase perceived social support among the caregivers (PROMIS Social Support short forms).

Hypothesis 5: Compared with baseline levels, we hypothesize that training in mindful communication reduce family conflict around caregiving (Family Conflict Scale).

Hypothesis 6: Compared with baseline levels, we hypothesize that mindfulness training will reduce anger and anxiety (PROMIS scales).

Hypothesis 7: Compared with baseline levels, we hypothesize that mindfulness training increase global self-perceived physical health (PROMIS short forms).

Hypothesis 8: Compared with baseline levels, we hypothesize that mindfulness training increase meaning and purpose (PROMIS short form).

Hypothesis 9: Compared with baseline levels, we hypothesize that mindfulness training along with a caregiver resources handbook will increase caregiver general and emotional self-efficacy (PROMIS scales).

Hypothesis 10: Compared with baseline levels, we hypothesize that mindfulness training will increase family satisfaction (Family Satisfaction Scale).

Hypothesis 11: Compared with baseline levels, we hypothesize that mindfulness training will increase mindfulness (Cognitive and Affective Mindfulness Scale).

**SPECIFIC AIM 3:** To explore comfort with and willingness to adopt technologies (e.g. telephone-based, web-based) to access mindfulness practices and existing caregiving educational resources.

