**Figure 2. Intervention design\***

\*In-person assessments and retreat were changed in March 2020 due to COVID pandemic

**SPECIFIC AIM 1:** To determine the feasibility and acceptability of a telephone-delivered mindfulness training intervention (TMT) in decreasing caregiver burden among informal caregiving teams caring for African Americans with dementia.

The primary outcomes are feasibility and acceptability among primary caregivers and also among care partners.

**SPECIFIC AIM 2:** To explore, on a preliminary basis, the effects of the training on caregiver burden and relevant secondary outcomes for both caregiving team members. Secondary outcomes include the following:

1. Pre-post intervention differences in caregiver burden (Zarit Burden Interview);
2. Pre-post intervention differences in coping emotion regulation and coping styles (Cognitive Emotion Regulation Questionnaire);
3. Pre-post intervention differences in tolerance of uncertainty (Intolerance of Uncertainty Scale);
4. Pre-post intervention differences in anger, anxiety, and global self-perceived health (PROMIS short forms);
5. Pre-post intervention differences in family satisfaction (Family Satisfaction Scale), perceived social support among the caregivers (PROMIS Social Support short forms) and family conflict around caregiving (Family Conflict Scale);
6. Pre-post intervention differences in caregiver self-efficacy;
7. Pre-post intervention differences in mindfulness (CAMS-R scale), hopefulness, and optimism (Meaning and Purpose Scale).

**SPECIFIC AIM 3:** To explore comfort with and willingness to adopt technologies (e.g. telephone-based, web-based) to access mindfulness practices and existing caregiving educational resources.

1. In interviews with both the primary caregivers and the care partners, we will investigate comfort and experience with internet devices, including smartphones, tablets, and computers. For half of the intervention groups, we will ask these questions in post-participation interviews, including exploring how individuals are currently using or would like to use these technologies (e.g., voice activation, use of bookmarks).
2. For half of the intervention groups, we will ask questions about technology before the intervention and will offer each family a tablet loaded with intervention materials, including the contents of the participant binder. Post-participation interviews will include questions about the ease of use and perceived value of the tablets.

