**Table 3: Questionnaire assessments**

Measure (construct)	Reliability, validity
Outcome: Zarit Burden Interview (ZBI) (distress associated with caregiving)	This 12-item (SF) version of the popular original 29-item questionnaire measures role strain ( $\alpha=0.88$ ) and personal strain ( $\alpha=0.77$ ) The short form was highly correlated with the original (0.96) both at baseline and follow-up.
Outcome and secondary stressor: Family Conflict Scale (Negative family interactions around caregiving)	The 4-item Family Conflict scale measures the degree of conflict the family experiences about the seriousness of the CR's condition, concerns about the CR's safety, what the CR can do for him/herself, and whether a nursing home is indicated.
Mediating outcome: Cognitive emotion regulation questionnaire (coping styles)	The 18-item short form of the CERQ measures 5 positive coping strategies (acceptance, positive refocusing, planning, positive reappraisal, putting into perspective) and 4 negative strategies (rumination, catastrophizing, self-blame, other-blame). Subscale reliability ( $\alpha=0.68-0.81$ ) and convergent validity was good.
Mediating outcome: Intolerance of Uncertainty Scale (discomfort with uncertainty)	The 12-item IUS correlates highly (0.96) with the original 27-item scale and results in a 2-factor (prospective, inhibitory) scale. Item responses range from 1 ( not at all characteristic of me ) to 5 ( entirely characteristic of me ). Its reliability was high for both the overall score ( $\rho=0.92$ ) and subscales and it demonstrated convergent validity. We will contact the scale developers to obtain permission

	to adjust to language of the responses to accommodate individuals without a high school education.
Mediating outcome: PROMIS social support measures (emotional, informational, instrumental support)	All three 4-item social support scales assess the frequency of perceived support with responses ranging from 1 ( Never ) to 5 ( Always ). Scoring is implemented in REDCap to preserve response pattern metrics.

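### Does the range of outcomes 3–11 in Section 9.5 leave the self-efficacy and family-satisfaction hypotheses without an analysis?

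*Combined protocol and SAP*

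**What the plan says.** Section 9.5 defines the quantitative analysis in one sentence: "For all quantitative questionnaire measures (outcomes 3-11), the change in the measure from baseline to post-participation is the outcome". It then plans a paired t-test per measure, with caregivers and care partners analysed separately, no multiplicity adjustment and a stated intention to interpret cautiously.

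The numbers refer to the secondary outcome list in Section 9.4.3. There, the last item inside the range is "11) Change in hopefulness and optimism as measured by the PROMIS meaning and purpose short form" and the next is "12) Change in caregiver self-efficacy as measured by the PROMIS self-efficacy short forms". Item 13, on willingness to adopt technologies, is marked qualitative. Family satisfaction does not appear.

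Elsewhere family satisfaction is treated as an outcome. In Section 1.2, Hypothesis 10 reads "we hypothesize that mindfulness training will increase family satisfaction (Family Satisfaction Scale"), and Section 9.1 repeats it. The secondary outcomes under Specific Aim 2 in Section 3 include "Pre-post intervention differences in family satisfaction (Family Satisfaction Scale"), with caregiver self-efficacy as the item after it.

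On coping, Hypothesis 2 refers to "increasing positive coping styles (acceptance, positive refocusing, positive reappraisal) and decreasing negative coping styles (rumination, catastrophizing, self-blame"). Table 3 describes the 18-item questionnaire as covering "5 positive coping strategies (acceptance, positive refocusing, planning, positive reappraisal, putting into perspective) and 4 negative strategies (rumination, catastrophizing, self-blame, other-blame").

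**The concern.** A reader who follows the numbers literally finds two hypotheses with nowhere to go: self-efficacy lies one place beyond the range, and family satisfaction is not in the list that the range refers to. With many scales, two roles and no multiplicity adjustment, a complete outcome list is a main protection against selective reporting. If these scales can be counted as inside or outside the plan, the team could decide after seeing the results whether to report them. The coping measure raises a similar worry. The hypothesis names three positive and three negative subscales, Table 3 groups five and four, and neither place says which score stands behind outcome 4.

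**Working it through.** No power or error-rate figure bears on this. The check is a mapping of hypotheses to outcomes.

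**Hypotheses (Sections 1.2 and 9.1) to outcome numbers (Section 9.4.3)**

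| Aim 2 hypothesis | Outcome no. | In 3–11? |
|---|---|---|
| 1 Burden | 3 | yes |
| 2 Coping | 4 | yes |
| 3 Uncertainty | 5 | yes |
| 4 Social support | 7 | yes |
| 5 Family conflict | 8 | yes |
| 6 Anger, anxiety | 9 | yes |
| 7 Physical health | 10 | yes |
| 8 Meaning and purpose | 11 | yes |
| 9 Self-efficacy | 12 | no |
| 10 Family satisfaction | none | no |
| 11 Mindfulness | 6 | yes |

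- Range 3–11: 9 of 11 hypotheses covered.
- Range 3–12: 10 of 11.
- Range 3–12 plus family satisfaction: 11 of 11.
- Scales outside the literal range: general self-efficacy, emotion-management self-efficacy and family satisfaction. That is 3 scales × 2 roles = 6 comparisons.

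**What the rest of the document says about those three scales**

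- *Self-efficacy.* The sentence in Section 9.5 claims all quantitative questionnaire measures and gives the numbers only in brackets. Outcome 12 is such a measure, and outcome 13 is the first qualitative item after it. Both parts of the sentence are true only if the range ends at 12, so the final number is a slip.
- *Family satisfaction.* Correcting the range does not bring it in, because it is missing from the list. It is, however, a hypothesis in Section 1.2 and again in Section 9.1 inside the statistical chapter, stated both times as change from baseline. Section 3 lists it as a pre-post secondary outcome. The Précis includes it in the baseline battery and has the questionnaires given again after the intervention. It too is a quantitative questionnaire measure, so the words of Section 9.5 reach it even though the numbers do not.

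**Coping subscales**

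- Hypothesis 2: 3 positive + 3 negative = 6.
- Table 3: 5 positive + 4 negative = 9.
- In the hypothesis but not in Table 3: none.
- In Table 3 but not in the hypothesis: planning, putting into perspective, other-blame, so 9 − 6 = 3.

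The six are a strict subset of the nine. Table 3 describes each instrument's content and psychometric properties; it assigns no subscale to a test and defines no composite. There are therefore not two competing scores for outcome 4. Table 3 reports reliability by subscale (alpha 0.68–0.81), and the hypothesis names individual subscales with a direction for each group, so subscale-level results are the natural reading.

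**The case for a change.** The strongest opposing case rests on family satisfaction. A wrong end-number cannot explain its absence from Section 9.4.3, and neither can its label in Table 3 as a process measure, because the mindfulness scale carries the same label and is listed as outcome 6. In an unadjusted exploratory analysis, an incomplete list leaves room to choose what is reported. On coping, the theory discussion in Section 2.2 uses planning as its example of a positive strategy that training might promote, yet Hypothesis 2 leaves planning out, and nothing says whether subscales or composites are tested. Correcting all of this would cost only wording, since the scales are already in the battery.

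Much of this is accurate. Section 9.4.3 is inconsistent with Sections 1.2, 3 and 9.1, and the coping score is not fully specified. What does not stand is the step to a missing analysis or an unlisted outcome: both measures are declared in advance as hypotheses and as Section 3 secondary outcomes, so the team could not drop them unnoticed or present them as new. Naming six coping subscales in advance, with directions, narrows the later choice. Prescribing two composites of those six would introduce a score that the documents do not mention, as one option among several.

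**Conclusion.** The observations about the lists are correct, but no change to the plan follows. The range in Section 9.5 stops one short, and Section 9.4.3 omits one scale that other sections list. Together these touch 2 of 11 hypotheses, or six comparisons. The plan's own text settles both in the same direction: analyse the change in every quantitative questionnaire measure with the same paired t-test. For coping, three of nine subscales have no stated role, which is detail that analysts can fill by reporting subscales and treating the six named ones as the content of Hypothesis 2.

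No result would differ. Aim 2 is declared exploratory, no adjusted error rate exists for extra scales to disturb, and feasibility, acceptability, the sample size and data collection are unaffected. Tidying the two lists would be an editorial courtesy.

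This rests on two assumptions: that the analysts read Section 9.5 together with Sections 1.2, 3 and 9.1, and that the Family Satisfaction Scale is collected at the final visit, as its listing as a pre-post outcome implies.

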### Qualitative variables

We will collect three types of formal qualitative data: 1) telephone interviews with key informants; 2) interviews with CG and CP prior to and following each 8-week class; and 3) transcriptions of audio-recorded classes. See key informant topics above. We will use the insights from key informants to adjust the intervention including the content and the logistics as needed.

Pre-participation interviews will address participant expectations and concerns about the research process in general and the intervention in particular.

Post-participation interviews will address CG/CP's attitudes and experiences with the intervention, including:

- The most memorable aspects of the class sessions;
- The perceived value and cultural congruence of the mindfulness training;
- The usefulness, challenges, and recommended changes in intervention components or language;
- The perceived value of various intervention components for management of stress related to caregiving or family conflict;
- Their recommendations for tools that might help maintain practices, if desired;
- Their unfulfilled expectations of the intervention;
- The usefulness of the technology components (e.g., call-in lines and/or tablets).

Each interview will be audio-recorded and transcribed. Using transcripts of key informant interviews and post-participation interviews, two or more research team members will apply a thematic analysis strategy, coding each transcript and identifying themes within and across interviews, with subsequent discussion of themes among members of the qualitative analysis team and resolution of discrepancies. The qualitative analysis team, who will include the PIs and [name], among others on the study team, will categorize the themes and present them to the Advisory Council for further input. Results will inform improvements in subsequent iterations of the intervention as well as the development of larger-scaled interventions.

## **10 DATA COLLECTION AND QUALITY ASSURANCE**

### **10.1 Data Collection Forms**

We will include data from multiple sources. For pre-post assessments with the caregiver, research assistants will collect demographic and questionnaire data on paper and input data into a secure, password-protected, web-based database for analysis. The research assistant will lock the paper case report forms in a portable filing cabinet until they can be transported to UNC for storage. The research assistant (RA) will follow a detailed Manual of Procedures for each aspect of data collection for each study visit and complete a visit checklist. On each checklist, the research assistant will document aspects of the visit that were completed, omitted (e.g., refused), and provide comments. Each checklist will be signed and dated by the RA and will become a CRF.

### **10.2 Data Management**

The UNC Program on Integrative Medicine will be responsible for all study staff and data collection. The study research assistant will collect data in the home of the caregiver and over the telephone for the care partner. UNC utilizes the REDCap database from which the study can download validated paper case report forms that correspond to the online database. All of the PROMIS measures are already available. Measures currently unavailable will be created with the assistance of the Clinical Data Manager at the North Carolina Translational and Clinical Sciences Institute.

**Program Fidelity.** With the permission of all participants, all program sessions will be audio-recorded. The purpose of the recording is two-fold: 1) to identify any systematic variations in instructors' attitude, communication, or behavior between groups and to screen for any group-dependent differences in communication in content or style between the instructors and participants; and 2) to capture participants' input and comments during the classes (for qualitative analysis). We will develop an evaluation matrix based on written protocols. [name] will listen to each program session to rate adherence to the protocol and will discuss deviations with the instructor, who may suggest changes to the intervention based on participant feedback.

### **10.3 Quality Assurance**

#### **10.3.1 Training**

All study staff will maintain up-to-date Good Clinical Practice, HIPAA, and Research Ethics training. Before participant data is collected, a PI or Project Manager will ensure that staff has completed training for applicable tasks. A log including dates and type of training will be kept in the Study Regulatory Binder.

The study's Manual of Operating Procedures (MOP) will include detailed procedures for each of the following:

- Consent forms:
  - Telephone/screening with detailed script and instructions included
  - Full Consent (detailed description in section 6.2 of protocol)

- HIPAA Consent
- REDcap data entry (used to track recruitment data, initial and post-intervention evaluations, study visits, and questionnaires)
- Interview techniques along with procedures for recording interview data
- Verbal and written administration of questionnaires.

#### 10.3.2 Quality Control Committee

The Quality Control Committee will consist of the project manager, the data manager, and the PIs. They will meet monthly to review data or process problems.

#### 10.3.3 Metrics

The data manager will audit 10% of the data entries each month in preparation for full team meetings of the study. She will identify and correct systematic errors in data entry by reviewing procedures with the research assistant. She will correct data entry errors using the original case report forms. If data entry error rates >10% persist, all data will be double entered.

#### 10.3.4 Protocol Deviations

Staff will be trained to record any protocol deviation that may occur while performing their specific research related activities. Many of the data collection forms will include comment sections to capture protocol deviation information. The project manager will document all protocol deviations in the secure online database, REDCap, as they occur. The entire study team will discuss deviations at monthly team meetings and report them to the IRB annually. Corrective action plans will be developed and submitted to the IRB as part of the reporting process

#### 10.3.5 Monitoring

The data manager (co-investigator) will review REDCap data for protocol compliance (including eligibility criteria) and audit data entry monthly within one month of the beginning of the first intervention group. This will include a biannual review of study instruments for range and consistency checks, and descriptive analyses to assess distributions of study variables. The project manager will review consent forms for completeness and institute remedial training for the research assistant as needed. The project manager is responsible for creating and reviewing the MOPs.

Quality assurance of qualitative measures (project manager) include 1) maintaining a database of scheduled, completed, transcribed, and analyzed classes and group evaluations; 2) establishing a transcription template to ensure data are uniform in appearance; 3) arranging for secure storage of recordings and transcripts; and 4) review of recordings to assess accuracy of transcriptions.

